**Table JZEA.10. Dose Modification Guidelines and AE Management for Toxicities At Least Possibly Related to Study Drug**

SOC	Toxicity	CTCAE Grade and/or Symptoms a		Treatment Plan b
		Grade	Symptoms	
Endocrine	Thyroid issues		If asymptomatic with TSH $<0.5 \times$ LLN or $>2 \times$ ULN	Continue study treatment; perform free T4 in subsequent cycles.
			If symptomatic	
 
Start thyroid replacement therapy and/or medical management and continue study treatment
 
For Grade 3 hyperthyroidism, withhold study treatment until hyperthyroidism improves to Grade <math>\leq 1</math>
 
For Grade 4 hyperthyroidism, discontinue study treatment
 

Endocrine	Hypotension, altered mental status, headache, fatigue, hyperglycemia		For endocrine issues other than thyroid issues (for example, hypophysitis)	
 
For Grade 2, withhold study treatment and administer prednisone 1 to 2 mg/kg/day
 
Resume study treatment when symptoms resolve and the patient is stable on hormone replacement therapy
 
For Grade 3 or 4, discontinue study treatment
 
For severe adrenal crisis, give stress dose of IV corticosteroids with mineralocorticosteroid
 

Gastrointestinal	Diarrhea, Abdominal pain, Blood in stool, Colitis	2		
 
Withhold study treatment, give anti-diarrheal medication, and check etiology
 
If the event continues for <math>>5</math> days despite the use of antidiarrheal medications, start prednisone 0.5 to 1 mg/kg/day
 
Resume study treatment after the event resolves to Grade <math>\leq 1</math>
 

SOC	Toxicity	CTCAE Grade and/or Symptoms a		Treatment Plan b
		Grade	Symptoms	
Gastrointestinal	Diarrhea, Ileus, Perforation, Colitis	≥3		
 
Withhold study treatment and administer prednisone 1 to 2 mg/kg/day (no corticosteroids if possible perforation)
 
If the event persists >3 days despite use of corticosteroids, add a nonsteroidal immunosuppressive agent and discontinue study treatment.c
 
Resume study treatment after the event resolves to Grade ≤1
 
Discontinue study treatment if Grade 3 persists
 
For Grade 4, discontinue study treatment
 

Hepatobiliary	Transaminitis, elevated bilirubin	2	
 
AST or ALT between <math>2.5 \times \text{ULN}</math> and <math>5 \times \text{ULN}</math>, or
 
TB between <math>1.5 \times \text{ULN}</math> and <math>3 \times \text{ULN}</math>
 
	
 
Withhold study treatment and administer prednisone 1 to 2 mg/kg/day
 
Resume study treatment after symptoms resolve to Grade ≤1
 

		≥3	
 
AST or ALT <math>>5 \times \text{ULN}</math>, or
 
TB <math>>3 \times \text{ULN}</math>
 
	
 
Discontinue study treatment and administer IV methylprednisolone 2 to 4 mg/kg/day
 
If the event continues for >3 days despite corticosteroids, add a nonsteroidal immunosuppressive agentc
 

Nervous system	Weakness, paresthesia (for example, Guillain–Barre syndrome or myasthenia gravis)		Moderate symptoms with no impact on ADL	Withhold study treatment until symptoms resolve.
	Instructions if vasculitis suspected: New onset loss of motor function	≥2 irAE	Impact on ADL	Discontinue study treatment. Give appropriate medical intervention and prednisone 1 to 2 mg/kg/day. 
 
Follow management guidelines above as clinically indicated
 
Consult neurologist/ rheumatologist, preferably with vasculitis expertise
 

SOC	Toxicity	CTCAE Grade and/or Symptoms a		Treatment Plan b
		Grade	Symptoms	
Respiratory	Pneumonitis	1		Consider withholding study treatment and monitoring for radiographic improvement.
		2	Mild to moderate symptoms	
 
Withhold study treatment and administer prednisone 1 to 2 mg/kg/day
 
Resume study treatment after the event resolves to Grade <math>\leq 1</math>
 

		$\geq 3$	Severe	
 
Discontinue study treatment and administer:           
 
IV methylprednisolone 2 to 4 mg/kg/day and prophylactic antibiotics
 
 
 
If the event remains at Grade <math>\geq 3</math> for <math>>2</math> days despite corticosteroids, add a nonsteroidal immunosuppressive agentc
 

	Instructions if vasculitis suspected: Hemoptysis, appearance of new lung nodules or rapidly progressing respiratory failure.			
 
Consult pulmonologist/rheumatologist with vasculitis expertise in addition to following management instructions above.
 
Signs of additional nodules and infiltrates (compared to baseline) from thoracic CT scans could be suggestive of vasculitis (See Section 9.4.2.1)
 

Cardiac	Myocarditis, cardiac function abnormalities (for example, dysrhythmia, valvular abnormalities)	$\geq 1$		
 
Discontinue study treatment and administer           
 
IV methylprednisolone 2 to 4 mg/kg/day
 
Consider immunosuppressives without immediate response to steroids (for example, mycophenolate, infliximab, or anti-thymocyte globulin)
 
 
 
Consult with cardiology immediately and; if available, transfer to cardiac care unit
 

SOC	Toxicity	CTCAE Grade and/or Symptoms a		Treatment Plan b
		Grade	Symptoms	
Renal and urinary	Elevated creatinine, decreased urine output, blood in urine, edema, nephritis	1	<1.5 x baseline	Continue study treatment
		2-3	1.5 × ULN < × ≤ 6 × ULN or >1.5 × baseline	
 
Withhold study treatment and administer prednisone 0.5 to 1 mg/kg/day
 
Resume study treatment after the event resolves to Grade ≤1
 
If elevations persist for >7 days or worsen, follow the guidelines for a Grade 4 event
 

		4	>6 × ULN	Discontinue study treatment and administer prednisone 1 to 2 mg/kg/day.
Skin	Instructions if vasculitis suspected: Elevated creatinine, decreased urine output, blood in urine, RBC casts, proteinuria		Creatinine: 1.5 × ULN < × ≤ 6 × ULN or >1.5 × baseline Proteinuria: >1+ on dipstick or regular urine analyses	
 
Follow management guidelines above as clinically indicated
 
Repeat creatinine and proteinuria and RBC casts in 7 days and if levels of creatinine and proteinuria still elevated and RBC casts still present, consult nephrologist and/or rheumatologist, preferably with vasculitis expertise. See Section 9.4.2.1.
 

	Rash, pruritus		Moderate rash (diffuse, ≤30% BSA)	
 
Withhold study treatment
 
For rash on <10% of the patient's BSA, administer intermediate or high-potency topical corticosteroid
 
For rash on 10%-30% of the patient's BSA, administer systemic corticosteroids
 
Resume study treatment if the rash improves to mild (localized) and the corticosteroid dose is <7.5 mg/day
 

	Instructions if vasculitis suspected: Palpable purpura, skin ulcers			
 
Follow management guidelines above as clinically indicated
 
Consult dermatologist/rheumatologist preferably with vasculitis expertise.
 
Confirmation of vasculitis with skin punch biopsy required ( See Section 9.4.2.1)
 

SOC	Toxicity	CTCAE Grade and/or Symptoms a		Treatment Plan b
		Grade	Symptoms	
Skin	Stevens–Johnson syndrome, toxic epidermal necrolysis, necrosis, bullous or hemorrhagic lesions			Discontinue study treatment and administer prednisone 1 to 2 mg/kg/day
Ophthalmological	Eye disorders (for example, uveitis, episcleritis)	≥2		
 
Consider topical steroids (for example, 1% prednisolone); temporarily discontinue study treatment until ophthalmology consult and administer           
 
Oral or IV methylprednisolone 2 to 4 mg/kg/day
 
 
 

	Instructions if vasculitis suspected: blurred vision, vision loss, periorbital swelling			
 
Follow management guidelines above as clinically indicated
 
Consult ophthalmologist/rheumatologist preferably with vasculitis expertise.
 
See Section 9.4.2.1.
 

Abbreviations: ADL = activities of daily living; ALT = alanine aminotransferase; AST = aspartate aminotransferase; BSA = body surface area; CRP = clinical research physician; CTCAE = Common Terminology Criteria for Adverse Events, version 5.0; irAE = immune-related adverse event; IV = intravenous; LLN = lower limit of normal; SOC = system organ class; TB = total bilirubin; TSH = thyroid-stimulating hormone; ULN = upper limit of normal.

- a If symptoms of grade is not specified, use CTCAE version 5.0 definitions; otherwise, use the definitions provided in this table.
- b Discontinuation of study treatment is permanent; resumption of study treatment is not allowed. If a toxicity does not resolve to Grade 0-1 or if the corticosteroid dose cannot be reduced to ≤10 mg/day of prednisone or equivalent within 12 weeks, consult with the Lilly CRP about discontinuing study treatment. In cases where corticosteroids are used, they should be appropriately tapered.
- c Immunosuppressive refers to infliximab or cyclophosphamide.

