**Table JZEA.8. Dose-Limiting Toxicity**

Hematologic toxicity

 
Grade 3 thrombocytopenia associated with clinically significant bleeding and requiring platelet transfusion or Grade 4 thrombocytopenia of any duration
 
Grade <math>\geq 3</math> febrile neutropenia
 
Grade <math>\geq 3</math> anemia requiring a blood transfusion
 
Other Grade 4 toxicity lasting <math>>7</math> days, excluding toxicities listed in Section 7.2.2.1
 

Nonhematologic toxicity – nonlaboratory

 
Grade 4 irAE, except as stated otherwise below
 
Grade <math>\geq 3</math> colitis or noninfectious pneumonitis
 
Other Grade 3 irAE, excluding colitis or pneumonitis, that: 
 
does not downgrade to Grade 2 within 3 days after onset of the event despite optimal medical management including corticosteroid therapy, or
 
does not downgrade to Grade <math>\leq 1</math> or the patient's baseline level within 14 days after onset of the event
 
 
 
Grade <math>\geq 3</math> pneumonitis or Grade 2 pneumonitis that does not show clinical improvement within 3 days after initiation of optimal medical management including corticosteroids therapy, which is then treated as Grade 3
 
Grade <math>\geq 3</math> toxicity despite optimal supportive care (e.g., nausea, vomiting, and diarrhea)
 
Grade <math>\geq 3</math> fatigue lasting <math>>7</math> days
 
Grade <math>\geq 3</math> hypertension despite maximal medical therapy
 

Nonhematologic toxicity – laboratory/investigations

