#### **7.2.2.2 DLT-Equivalent Toxicities**

A DLT-equivalent toxicity (ET) is an AE that meets the DLT criteria as defined above and occurs in any cycle other than the DLT assessment period (28 days for Q2W schedule and 42 days for Q3W schedule). In addition to the DLT assessment period, available safety data beyond the DLT assessment period may also be taken into consideration prior to a decision to advance to the next dose level or the determination of the RP2D.

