### 7.4. Dose Modification

No dose modification is allowed during the DLT observation period (Cycle 1). See Section 8 for discontinuation criteria. See Section 7.6.1.1 for the definition of DLT-evaluable patients.

After the DLT observation period (Cycle 1), doses of the study drug may be delayed or discontinued to manage specific AEs or other toxicities. Dose reductions are not permitted. All dose modifications should be documented, including the approach taken and a clear rationale for the need for modification.

The investigator must assess whether the toxicity is at least possibly due to study treatment and apply the dose-modification guidelines. Investigators are encouraged to consult Lilly for additional guidance.

If a patient requires a dose delay, study treatment should be resumed within 1 cycle, if possible and appropriate. If study treatment cannot be resumed within 1 cycle, every effort should be made to restart on the first day of the next cycle. In rare circumstances, a delay of >28 days may be permitted before permanent treatment discontinuation, as long as the patient demonstrates clinical benefit, does not have objective progression, and is recovering from the toxicity. Such circumstances must be discussed with the Lilly CRP/CRS.

Adverse events of immune-related etiology are expected because of the study drug's mechanism of action and may occur shortly after the first dose or several months after the last dose. Study treatment must be withheld if the patient experiences a drug-related toxicity or a severe or life-threatening AE. Dose reductions are not permitted.

A 4-hour observation period following the end of LY3434172 administration will occur in Cycles 1 to 3. During observation period, patients treated with LY3434172 should be closely monitored for signs and symptoms indicative of an infusion-related reaction by medical staff from the start of the infusion, in an area where emergency medical resuscitation equipment and other agents (epinephrine, prednisolone, or equivalents, etc.) are available. LY3434172 infusion-related reactions will be defined according to the Common Terminology Criteria for Adverse Events (CTCAE), version 5.0 definition of IRRs.

Table JZEA.9 presents instructions for management of infusion-related reactions associated with LY3434172.

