### 8.1. Discontinuation from Study Treatment

Patients will be discontinued from study treatment in the following circumstances:

- the patient is enrolled in any other clinical study involving an investigational product or any other type of medical research judged not to be scientifically or medically compatible with this study.
- the patient becomes pregnant during the study
- the patient is significantly non-compliant with study procedures and/or treatment as described in Section 7.6
- The patient experiences a DLT (see Section 7.2.2.2) during Cycle 1, a DLT-ET (see Section 7.2.2.2.2), or other unacceptable toxicity
- the patient requires a dose delay of >28 days for Q2W schedule and >21 days for Q3W schedule, except as described in Section 7.4
- the patient, for any reason, requires treatment with another therapeutic agent that has been demonstrated to be effective for treatment of the study indication. Discontinuation from study treatment will occur prior to introduction of the new agent
- the investigator decides that the patient should be discontinued from study treatment, for reasons such as but not limited to confirmed disease progression (see Section 9.1.1).
- the patient requests to be discontinued from study treatment

Patients who are discontinued from study treatment will have follow-up procedures performed as shown in the Schedule of Activities (Section 2).

Discontinuation of study treatment may be considered for patients who meet all of the following criteria:

- have a confirmed complete response (CR), **and**
- have received study treatment for at least 24 weeks, **and**
- have received at least 2 cycles of study treatment beyond the date when the initial CR was declared.

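### After the DLT period, Grade 3 colitis that settles promptly is told both to resume and to stop; in Cohorts A7/A8 a DLT on days 22 to 42 has no DLT-specific stopping rule

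*Protocol*

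**What the plan says.** **Colitis.**

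- Protocol Table JZEA.8 lists Grade ≥3 "colitis or noninfectious pneumonitis" as a DLT and attaches no duration or recovery condition. The next bullet gives other Grade 3 immune-related events 3-day and 14-day recovery windows and expressly leaves colitis out. Section 7.2.2.2 adds that the event must be clinically significant and at least possibly related.
- A DLT-equivalent toxicity (DLT-ET, Section 7.2.2.2.2) meets the same criteria and "occurs in any cycle other than the DLT assessment period (28 days for Q2W schedule and 42 days for Q3W schedule".
- Section 8.1 is mandatory. One trigger for stopping treatment reads "The patient experiences a DLT (see Section 7.2.2.2) during Cycle 1, a DLT-ET (see Section 7.2.2.2.2), or other unacceptable toxicity". Footnote b of Table JZEA.10 makes discontinuation permanent.
- The Grade ≥3 gastrointestinal row of Table JZEA.10 covers diarrhea, ileus, perforation and colitis. It withholds treatment, gives prednisone, and stops treatment for Grade 4, for Grade 3 that persists, or for an event lasting more than 3 days despite corticosteroids. Otherwise: "Resume study treatment after the event resolves to Grade \leq 1". On use of the table, Section 7.4 says: "The investigator must assess whether the toxicity is at least possibly due to study treatment and apply the dose-modification guidelines".

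**Cohorts A7/A8.**

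- Section 7.2.1 sets the Q3W cycle at 21 days. Section 7.2.2.2 sets the A7/A8 DLT window at Cycles 1 and 2, 42 days.
- The discontinuation sentence in Section 7.2.2.2 names A7 and A8 but applies to a DLT in Cycle 1. The Section 8.1 trigger above has the same limit.
- Section 7.4 says "No dose modification is allowed during the DLT observation period (Cycle 1). See Section 8 for discontinuation criteria", and repeats the Cycle 1 label when it says from when delays are allowed.
- Protocol Section 10.3.1 summarizes DLTs occurring in Cycle 1. SAP Section 6.2.1 labels the DLT observation period Cycle 1.

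**The concern.** A site treating Grade 3 colitis will read Table JZEA.10; a monitor checking discontinuations will read Section 8.1. For an event that settles promptly after the DLT period, the two give opposite answers. Two sites could handle the same patient differently. One of them could re-expose the patient to a first-in-human bispecific at full dose, since no reductions are allowed, after an event the protocol itself classes as dose-limiting.

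In A7/A8, an event can count as a DLT and still trigger no DLT-specific stop, because the window was set at 42 days while the stopping wording stayed at Cycle 1. The same shorthand in Section 10.3.1 could drop such events from the DLT summary, and DLTs are a primary endpoint.

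**Working it through.** The plan gives no figure of its own to reproduce and no event rate. The check is a cross-reading plus day counts.

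**Step 1. Related, clinically significant Grade 3 colitis after the DLT period.**

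| Course of event | Table JZEA.10 | Section 8.1 |
|---|---|---|
| Grade 4, persistent Grade 3, or >3 days despite corticosteroids | Discontinue | Discontinue (DLT-ET) |
| Settles promptly to Grade ≤1 | Resume | Discontinue (DLT-ET) |

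Only the second line conflicts. Grade ≥3 pneumonitis shares the colitis bullet in Table JZEA.8, and its Table JZEA.10 row says discontinue, which agrees with Section 8.1.

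**Step 2. How far other rules narrow the resume route.**

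Inputs:
- Dosing interval I = 14 days (Q2W) or 21 days (Q3W), Section 7.2.1.
- Longest permitted delay L = 28 days (Q2W) or 21 days (Q3W), Section 8.1.
- Taper T = 1 month, starting at Grade ≤1 and finished before restart, Section 7.4. I take 28 to 31 days (assumption).
- t = days from last dose to Grade ≤1.

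The documents do not say when a delay starts. Counting from the missed scheduled dose:

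delay = t + T − I, which must not exceed L, so t ≤ I + L − T.

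- Q2W: I + L = 14 + 28 = 42.
- Q3W: I + L = 21 + 21 = 42.
- T = 28: t ≤ 14. T = 30: t ≤ 12. T = 31: t ≤ 11.

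If the delay ran from the last dose instead, t ≤ L − T. With T = 28 that is 28 − 28 = 0 (Q2W) or 21 − 28 = −7 (Q3W), and the route is closed. The first convention is therefore the more permissive one. A later restart needs the exception in Section 7.4, which requires clinical benefit, no objective progression, recovery under way and discussion with the sponsor.

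**Step 3. Which stopping rule reaches a DLT after Cycle 1.**

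| Cohorts | Cycle 1 | DLT window | In window, after Cycle 1 | DLT-ET begins after | DLT-specific stop for those days |
|---|---|---|---|---|---|
| A2 to A6 | 28 days | 28 days | none | day 28 | not needed |
| A1 | 28 days | 42 days | days 29 to 42 (42 − 28 = 14 days) | day 28 | yes, as DLT-ET |
| A7/A8 | 21 days | 42 days | days 22 to 42 (42 − 21 = 21 days) | day 42 | none |

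For A7/A8, 21/42 is half the window. Infusions fall on Day 1, Day 1 + 21 = 22 and Day 22 + 21 = 43, so one of the two infusions in the window is in the uncovered half. At a minimum of three patients per cohort (Section 5.2), 2 × 3 = 6 patients or more are concerned.

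**Step 4. The DLT summary.** Taken literally, Section 10.3.1 omits DLTs on days 22 to 42 in A7/A8 and on days 29 to 42 in A1. The A1 part uses the 28-day cycle of Section 7.2.1; Section 7.2.2.2 labels A1's whole 42 days as Cycle 1.

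**The case against.** The best case for the plan is that the order of authority is already clear. Section 8.1 is mandatory, and Sections 7.2.1 and 7.4 both point to Section 8. Table JZEA.10 is offered as guidelines that local standards may replace. The resume bullet also has a proper use: Grade 3 diarrhea counts as a DLT only as "toxicity despite optimal supportive care (e.g., nausea, vomiting, and diarrhea", so a case that responds is not a DLT-ET and may restart. Much of this stands, and I agree that Section 8.1 probably governs. But nothing says so at the row, which does not separate colitis from responsive diarrhea. The provisions on local standards and the ASCO guideline allow departure from the table; they do not waive Section 8.1. Where Section 8.1 means to yield to Section 7.4 it says so, as in "the patient requires a dose delay of >28 days for Q2W schedule and >21 days for Q3W schedule, except as described in Section 7.4". The DLT-ET trigger has no such clause.

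On A7/A8, a Cycle 2 DLT can still be stopped through the unacceptable-toxicity wording or by investigator decision in Section 8.1, and several severe events have their own discontinue instruction in Table JZEA.10. That is true, but the first two are judgements and the table does not cover every DLT.

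A reader might infer that Section 7.4 frees the Day 22 infusion from the dose-modification ban. The text does not go that far. The operative term is the DLT observation period, defined as 42 days for A7/A8; the Cycle 1 label makes it ambiguous, no more.

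On the summaries, the DLT-equivalent table in Section 10.3.1 covers any period of the study, so the events would appear somewhere. SAP Section 6.12.2 takes its definitions from Protocol Sections 7.2.2.2 and 7.6.1, so the SAP label is largely harmless.

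**Conclusion.** Both parts hold and should be corrected. The colitis conflict is real but narrow: Grade 3, related, clinically significant, after the DLT period, and mainly back to Grade ≤1 within about 11 to 14 days of the last dose, or allowed through under the Section 7.4 exception. That range rests on a 28- to 31-day taper and on counting delay from the missed dose. The A7/A8 gap covers 21 of 42 days and one of two infusions, in at least 6 patients.

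Stronger readings are not supported:
- A reader might infer that patients can be freely re-dosed after Grade 3 colitis. The row's own stops, the taper and the delay limits prevent that, and Section 8.1 probably forbids it altogether.
- A reader might infer that A7/A8 patients must continue after a Cycle 2 DLT. Nothing requires it.
- Half the window is a share of calendar time, not of risk. With no event rates in the documents, no percentage of patients can be given.
- Dose finding is not distorted. DLTs are determined under the windows in Section 7.2.2.2, so DLT determinations and mTPI-2 decisions do not change.

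What is at stake is patient safety, consistent handling across sites, and a literal gap in one DLT table.

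**What to change.** 1. In Table JZEA.10, state that Section 8.1 governs whenever the event is a DLT or DLT-ET. The resume bullet in the Grade ≥3 gastrointestinal row then applies only to events that are not DLT-ETs, such as Grade 3 diarrhea that responds to supportive care. If rechallenge after Grade 3 colitis is wanted, name it as an exception in the DLT-ET bullet of Section 8.1.
2. Replace *Cycle 1* with *the DLT observation period* in the discontinuation sentence of Section 7.2.2.2, the Section 8.1 bullet and the DLT bullet of Section 10.3.1. Align SAP Section 6.2.1.
3. In Section 7.4, delete the two *(Cycle 1)* labels only together with a statement that withholding a dose for safety under Table JZEA.10 is always allowed, with DLT evaluability then decided under Section 7.6.1.1. Deletion alone would put the Day 22 infusion firmly under the ban, against the instructions in Section 7.4 and Table JZEA.10 to withhold for drug-related toxicity. Because Section 7.6.1.1 defines dose escalation as A1 to A5/A6, say that it also applies to A7/A8.

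The cost is wording in the protocol and one phrase in the SAP, with no added procedures. Patients with Grade 3 colitis lose rechallenge unless the sponsor names the exception. A patient without a DLT whose Day 22 dose is withheld would not be evaluable under Section 7.6.1.1 and might be replaced.
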